2.9.3 Vital signs

The summary of vital signs will only include on treatment data, which are defined as those vital sign measurements after the first dose of study treatment and on or before last dose + 84 days.

[figure not shown]
Analysis in vital sign measurement using descriptive summary statistics for the change from baseline for each post-baseline visit will be performed. These descriptive summaries will be presented by vital sign and treatment group. Change from baseline will only be summarized for subjects with both baseline and post-baseline values and will be calculated as:

[figure not shown]
$$\text{change from baseline} = \text{post-baseline value} - \text{baseline value}$$

[figure not shown]
The number and percentage of subjects with newly occurring notable vital signs will be presented. Criteria for notable vital sign abnormalities are provided in [Table 2-4](#) below.

Table 2-4 Criteria for notable vital sign abnormalities

Vital sign (unit)	Notable abnormalities
Systolic blood pressure (mmHg)	>= 140 mmHg or < 90 mmHg
Diastolic blood pressure (mmHg)	>=90 mmHg or <60 mmHg
Pulse (bpm)	> 100 bpm or <60 bpm

2.12.3 Efficacy Evaluation

2.12.3.1 Description of efficacy variables

ACR 20/50/

ACR20 is a binary response variable defined for each subject. A subject will be considered a responder according to ACR20 criteria if he/she has at least (i.e., \geq):

- 20% improvement from baseline in tender 78-joint count
- 20% improvement from baseline in swollen 76-joint count
- 20% improvement from baseline in at least 3 of the following 5 measures:
 - Patient's assessment of PsA pain (VAS 100 mm)
 - Patient's global assessment of PsA disease activity (VAS 100 mm)
 - Physician's global assessment of PsA disease activity (VAS 100 mm)
 - Patient self-assessed disability (Health Assessment Questionnaire [HAQ[©]] score)
 - Acute phase reactant (C-reactive protein [hsCRP]) **or** Erythrocyte sedimentation rate (ESR).

In the definition above, the *baseline* value refers to the last measurement made prior to administration of the first dose of study treatment.

The primary endpoint is the proportion of subjects achieving ACR20 at Week 52. Primarily, CRP will be used to calculate ACR response: ESR will only be used in the event CRP is missing.

ACR50 are defined in the same way as ACR20 by replacing the 20% with 50% and 70% improvement from baseline, respectively.

ACR_n represents the percent improvement on the continuous scale and from ACR_n one can directly calculate ACR20, ACR50, using the appropriate cutoffs. This variable is defined as:

$ACR_n = \min(x_1, x_2, x_3)$, where

$x_1 =$ % improvement from baseline in tender 78-joint count

$x_2 =$ % improvement from baseline in swollen 76-joint count

and $x_3 =$ 3rd largest value of x_4, x_5, x_6, x_7, x_8 where,

$x_4 =$ % improvement from baseline in Patient's assessment of PsA pain (VAS 100 mm)

$x_5 =$ % improvement from baseline in Patient's global assessment of PsA disease activity (VAS 100 mm)

x_6 = % improvement from baseline in Physician's global assessment of PsA disease activity (VAS 100 mm)

x_7 = % improvement from baseline in Patient self-assessed disability (Health Assessment Questionnaire [HAQ©] score)

x_8 = % improvement from baseline in Acute phase reactant (C-reactive protein [hsCRP])
or Erythrocyte sedimentation rate (ESR)

ACRn can be computed even if up to two values of x_4 , x_5 , x_6 , x_7 , x_8 are missing. ACRn, theoretically, cannot be computed, if one or both of x_1 , x_2 is/are missing OR more than three values of x_4 , x_5 , x_6 , x_7 , x_8 are missing.

Health Assessment Questionnaire - Disability Index (HAQ-DI)

The Health Assessment Questionnaire (HAQ©) was developed by Stanford University and is one of the most widely used measures to assess the long-term influence of chronic disease on a subject's level of functional ability and activity restriction. The disability assessment component of the HAQ (Health Assessment Questionnaire – Disability Index), the HAQ-DI, assesses a subject's level of functional ability and includes questions of fine movements of the upper extremity, locomotor activities of the lower extremity, and activities that involve both upper and lower extremities. There are 20 questions in eight categories of functioning including dressing, rising, eating, walking, hygiene, reach, grip, and usual activities. The stem of each item asks over the past week "Are you able to ..." perform a particular task. Each item is scored on a 4-point scale from 0 to 3, representing normal (normal, no difficulty [0]), some difficulty [1], much difficulty [2], and unable to do [3].

Scoring for the eight functional categories and overall disability index scoring will be performed as follows:

There are eight categories; first score within each category:

- Dressing and Grooming, includes items 1 and 2
- Arising, includes items 3 and 4
- Eating, includes items 5, 6 and 7
- Walking, includes items 8 and 9
- Hygiene, includes items 10, 11, and 12
- Reach, includes items 13 and 14
- Grip, includes items 15, 16 and 17
- Activities, includes items 18, 19, and 20

The score for each category will be the single response within the category with the highest score (greatest difficulty). For example, in the "Eating" category, there are two answers (one for each item). If "Cut your food with a knife or fork" is marked as "3" and "Lift a full cup or glass to your mouth" is marked as "0", then the score for the "Eating" category would be "3" (the response indicating the greatest difficulty within the category). If a component question is left blank or the response is too ambiguous to assign a score, then the score that that category will be determined by the remaining completed question(s). However, if **any** "aids or devices"

[figure not shown]
and/or "help from another person" items at the bottom of each page are checked, the category to which they apply will be adjusted upward to "2". If the basic score is **already** "2" or "3", the score remains unchanged. "Aids or devices" and "help from another person" can **only** change a category's score to "2"; they do **not** change the score to a "1" or a "3".

[figure not shown]
The score for the disability index will be the mean of the eight category scores. If more than two of the categories, or 25%, are missing, scale will not be scored. Otherwise, divide the sum of the categories by the number of answered categories. The higher score indicates greater disability.

There are two definitions for **HAQ-DI response** that will be used for analysis:

Definition 1: an improvement of at least 0.3 score points compared to baseline.

Definition 2: an improvement of at least 0.35 score points compared to baseline.

ACR Components

Tender 78 joint count and swollen 76 joint count

The 78 joints assessed for tenderness include the 2 temporomandibular, 2 sternoclavicular, 2 acromioclavicular joints, 2 shoulders, 2 elbows, 2 wrists, 2 first carpometacarpal, 10 metacarpophalangeal, 10 proximal interphalangeal, 8 distal interphalangeal joints of the hands, the 2 hip, 2 knee, 2 talo-tibial, 2 mid-tarsal, 10 metatarsophalangeal, 10 proximal interphalangeal, and 8 distal interphalangeal joints of the feet. All of these except for the hips are assessed for swelling. Joint tenderness and swelling are to be graded present (1) or absent (0). Synovial fluid and/or soft tissue swelling but not bony overgrowth represents a positive result for swollen joint count. Dactylitis of a digit in the foot or hand counts as one tender and swollen joint.

If the number of joints for which data were available (e.g., T) is less than 78/76 for the tender/swollen joint assessment, the number of tender/swollen joints (e.g., t) will be scaled up proportionately (i.e., $78*t/T$ or $76*t/T$ for tender or swollen joint count).

Patient's assessment of PsA Pain

The patient's assessment of pain will be performed using 100 mm visual analog scale (VAS) ranging from "no pain" to "unbearable pain" after the question "*Please indicate with a vertical mark (|) through the horizontal line the most pain you had from your psoriatic arthritis today*".

Patient's global assessment of PsA disease activity

The patient's global assessment of disease activity will be performed using 100 mm VAS ranging from "very good" to "very poor", after the question "*Considering all the ways psoriatic arthritis affects you, please indicate with a vertical mark (|) through the horizontal line how well you are doing today*".

Physician's global assessment of PsA disease activity

[figure not shown]
The physician's global assessment of disease activity will be performed using 100 mm VAS ranging from no disease activity to maximal disease activity, after the question "*Considering all the ways the disease affects your patient, draw a line on the scale for how well his or her condition is today*". To enhance objectivity, the physician must not be aware of the specific patient's global assessment of disease activity, when performing his own assessment on that patient.

[figure not shown]
Erythrocyte sedimentation rate (ESR)

Blood for ESR, which is helpful in diagnosing inflammatory diseases and is used to monitor disease activity and response to therapy, will be obtained at scheduled visits.

High-sensitivity C-reactive protein (hsCRP)

[figure not shown]
Blood for this assessment will be obtained in order to identify the presence of inflammation, to determine its severity, and to monitor response to treatment. Since the results of this test may unblind study personnel, results from the central lab will be provided for screening and baseline only. The hsCRP results from samples collected during the treatment period will be revealed following database lock only.

Presence of enthesitis

If enthesitis based on LEI is present with any of the 6 sites (lateral epicondyle humerus L + R, proximal achilles L + R and medial condyle femur L + R), the patient is counted as a patient with enthesitis.

Resolution of enthesitis

Resolution of enthesitis (based on LEI [REDACTED]) is defined as absence of enthesitis at any post-baseline visit in subjects included in the Enthesitis subset (LEI [REDACTED]).

Psoriasis Area and Severity Index (PASI)

The PASI assessment will be conducted for subjects in whom at least 3% of the body surface area (BSA) was affected by psoriatic skin involvement at baseline. The PASI assesses the extent of psoriasis on four body surface areas (head, trunk and upper and lower limbs) and the degree of plaque erythema, scaling and thickness. A PASI score will be derived as indicated in [Table 2-7](#). The head, trunk, upper limbs and lower limbs are assessed separately for erythema, thickening (plaque elevation, induration), and scaling (desquamation). The average degree of severity of each sign in each of the four body regions is assigned a score of 0-4. The area covered by lesions on each body region is estimated as a percentage of the total area of that particular body region. Further practical details help the assessment:

1. The neck is assessed as part of the head.
2. The axillae and groin are assessed as part of the trunk.

3. The buttocks are assessed as part of the lower limbs.
4. When scoring the severity of erythema, scales should not be removed.

Table 2-7 The PASI scoring system

Body region	Erythema (E)	Thickening (plaque elevation, induration, I)	Scaling (desquamation) (D)	Area (based on true area %, A)*	score
Head (H)**	0=none	0=none	0=none	0	= no
	1=slight	1=slight	1=slight		involvement
	2=moderate	2=moderate	2=moderate	1 = >0-< 10%	
	3=severe	3=severe	3=severe	2 = 10-<30%	
	4=very severe	4=very severe	4=very severe	3 = 30-<50%	
				4 = 50-<70%	
Trunk, (T)***	0=none	0=none	0=none	0	= no
	1=slight	1=slight	1=slight		involvement
	2=moderate	2=moderate	2=moderate	1 = >0-< 10%	
	3=severe	3=severe	3=severe	2 = 10-<30%	
	4=very severe	4=very severe	4=very severe	3 = 30-<50%	
				4 = 50-<70%	
Upper limbs (U)	0=none	0=none	0=none	0	= no
	1=slight	1=slight	1=slight		involvement
	2=moderate	2=moderate	2=moderate	1 = >0-< 10%	
	3=severe	3=severe	3=severe	2 = 10-<30%	
	4=very severe	4=very severe	4=very severe	3 = 30-<50%	
				4 = 50-<70%	
Lower limbs (L)****	0=none	0=none	0=none	0	= no
	1=slight	1=slight	1=slight		involvement
	2=moderate	2=moderate	2=moderate	1 = >0-< 10%	
	3=severe	3=severe	3=severe	2 = 10-<30%	
	4=very severe	4=very severe	4=very severe	3 = 30-<50%	
				4 = 50-<70%	
			5 = 70-<90%		
			6 = 90-100%		

Percentage (not score) of body region (not whole body) affected will be entered in the eCRF

**Neck is assessed as part of the Head (H) body region.

***Axillae and groin are assessed as part of the Trunk (T) body region.

[figure not shown]
****Buttocks are assessed as part of the Lower limbs (L) body region.

[figure not shown]
Because the head and neck, upper limbs, trunk and lower limbs correspond to approximately 10%, 20%, 30% and 40% of the body surface area, respectively, the PASI score is calculated using the formula:

[figure not shown]
$$\text{PASI} = 0.1(\text{E}_H + \text{I}_H + \text{D}_H)\text{A}_H + 0.2(\text{E}_U + \text{I}_U + \text{D}_U)\text{A}_U + 0.3(\text{E}_T + \text{I}_T + \text{D}_T)\text{A}_T + 0.4(\text{E}_L + \text{I}_L + \text{D}_L)\text{A}_L$$

[figure not shown]
The keys for the letters are provided in [Table 2-7](#).

[figure not shown]
PASI scores can range from a lower value of 0, corresponding to no signs of psoriasis, up to a theoretic maximum of 72.0. The total score comes from eCRF.

3 Sample size calculation

A family-wise error will be set to two-sided $\alpha=0.05$ to control for type I error. The primary objective of secukinumab 300 mg versus adalimumab with respect to ACR50/ACR20 response at Week 52 will be tested at a two-sided 0.05 alpha level.

An ACR20 response rate of about 50% for the TNF α inhibitor naïve without MTX use (monotherapy) population at week 48 was reported in Humira study ([Gladman 2007](#)). The response on secukinumab 300 mg is estimated to be 62% in the TNF α inhibitor naïve monotherapy population based on the lower bound of 80% confidence interval of Meta-analysis results of the study FUTURE2 ([McInnes 2015](#)) and unpublished study FUTURE3. With 425 subjects per treatment group there would be approximately 94% power to detect a treatment difference of 12% at a two-sided 0.05 alpha level in ACR20 response rates (Chi Square test, NQuery 7.0) between secukinumab 300 mg and adalimumab in the evaluation of the primary efficacy hypothesis at Week 52. The overall sample size will be 850 patient for a randomization ratio of 1:1 (secukinumab 300mg 425 patients, and adalimumab 425 patient). The estimated power with the chosen sample size for other efficacy endpoints based on the data available for adalimumab and meta-analysis results of the study FUTURE2 and study FUTURE3 are summarized in [Table 3-2](#).

Table 3-1 Assumption for sample size and power calculation

Endpoint	Secukinumab 300 mg expected values	Adalimumab (N=76) observed values
ACR20	62%	50%
PASI90	63%	38% (N=40)
ACR50	49%	38%
HAQ-DI change*	-0.59 (0.5)	-0.4 (0.5)(N=61)
Resolution of enthesitis	61%	33%

*mean (standard deviation)

Sources: The value for Secukinumab is from the lower bound of 80% confidence interval of a meta-analysis based on FUTURE2 and unpublished results from FUTURE3 data, the values for other endpoints for Secukinumab are from the means of the same meta-analysis, the values for Adalimumab are from Humira® study ([Gladman 2007](#)).

Based on [Table 3-1](#), power calculation for superiority tests of different endpoints are presented below in [Table 3-2](#).

[figure not shown]
Table 3-2 Power for superiority tests for primary and secondary endpoints (two-sided, $\alpha=0.05$)

[figure not shown]
Endpoint	Power*
ACR20 (H1)	94%
PASI90 (H2)	99%
ACR50 (H3)	91%
HAQ-DI (H4)	99%
Resolution of enthesitis (H5)	99%

* power does not consider dependence of the endpoints in the Testing Strategy, power for PASI90 and enthesitis is based on the assumption that a subset of half of the population (213 subjects per group) has data of these two endpoints.

4 Change to protocol specified analyses

All the analysis specified in the protocol for CSR is detailed in this SAP.

6 Appendix

6.1 Visit Windows

When visit windows are used, all visits will be re-aligned, i.e., they will be mapped into one of the visit windows. E.g., if the Week 4 visit of a subject is delayed and occurs on Day 46 instead of scheduled Day 29, say, it will be re-aligned to visit window *Week 8*. In the case of major deviations from the visit schedule, or due to unscheduled visits, several assessments of a subject may fall in a particular visit window (either scheduled or unscheduled).

For lab/ECG/vital signs, follow-up (F/U) visit is excluded from analysis visit mapping window. Only assessments that come as F/U nominal visit will be directly assigned as analysis F/U visit. Other assessments that are beyond the last on-treatment visit window (W50) or after nominal F/U visit date won't be mapped to any analysis visit. F/U visit will not be included in the summary tables by visit.

Of note, subjects are allowed to have gaps in visits. All data collected will be displayed in listings.

Table 6-1 Analysis Visit Windows

Analysis Visit	Group 1	Group 2	Group 3	Group 4	Group 5	Group 6	Group 7	Group 8
Baseline	≤1*	≤1*	≤1*	≤1*	≤1*	≤1*	≤1*	≤1*
Week 2	2 – 26				2 - 26			
Week 4	27 – 50	2 - 134		2 - 71	27 - 50			2-50
Week 8	51 – 78				51 - 78			51 – 78
Week 12	79 – 106		2 - 148	72 - 106	79 - 106	2 - 148		79 – 106
Week 16	107 – 134			107 - 155	107 - 155			107 – 134
Week 20	135 – 162							135 – 162
Week 24	163 – 190	135 - 316	149 - 316	156 - 211	156 - 211	149 - 211	2 - 316	163 – 190
Week 28	191 – 218							191 – 218
Week 32	219 – 246			212 - 267	212 - 267	212 - 267		219 – 246
Week 36	247 – 274							247 – 274
Week 40	275 – 302			268 - 344	268 - 344	268 - 344		275 – 302
Week 44	303 – 330							303 – 330
Week 48	331 – 358							331 – 358
Week 52	359 – 498	317 - 449	317 - 498	345 - 498	345 - 498	345 - 498	317 - 449	359 – 498
Week 68		450 - 498					450 - 498	

* The first administration of randomized study treatment (first dose) is defined as Day 1.

Group1: ACR components, ESR, High sensitivity C-Reactive protein

Group2: [REDACTED]

Group3: Hematology, blood chemistry, urinalysis, Lipids, [REDACTED]

Group4: [REDACTED]

Group5: LEI, [REDACTED], PASI, [REDACTED]

Group6: Urine pregnancy test

Group7: [REDACTED]

Group8: Vital signs

The following rules are used to determine the window for an applicable visit post baseline: “Lower limit” = “upper limit of prior applicable visit” + 1. Upper Limit = 0.25*(Week number of current visit)* 7 + 0.75 * (Week number of next applicable visit)*7 + 1. Lower limit of the first applicable visit is always Day 2.

The mapping described above applies to all visits (not just scheduled visits). Repeat and/or unscheduled visits (which will be numbered in the database according to new NCDS standards) will be mapped for analysis purposes in the same way as scheduled visits. This leaves the possibility, then, for multiple measurements within an analysis window. Taking into account the fact that the protocol stipulation is “the study treatment should not be administered less than 14 days from the previous administration” and bi-weekly dosing schedule for Adalimumab, which leads to all visit delays accumulative, the following rule will be used to determine the appropriate measurement to be summarized in the event of multiple measurements within a visit window.

Table 6-2 Rules for flagging variables

Timing of measurement	Type of data	Rule
Baseline	All data	
The last non-missing measurement made prior to or on the date of administration of the first dose of study treatment (the reference start date / Day 1). If a patient did not receive any dose of study treatment then the randomization date will be used. Only date part is considered if just one assessment on Day 1.
 
If there are multiple assessments on Day 1, following rules will apply:
 
 (a) If assessment time exists, 
 - select the last available measurement prior to reference start date/time considering time; - if no measurement prior to reference start date/time considering time, select the earliest measurement post reference start date/time considering time . (b) If assessment time does not exist, select the available measurement from the lowest CRF visit number.
Post-baseline efficacy	All data	
 • The last assessment within the window will be used. • Cases where the same parameter is recorded more than once on the same date will be handled as follows: 
 ○ If time of completion exists the earliest measurement will be used; ○ If time does not exist the measurement from the lowest CRF visit number will be used.
Post-baseline safety	Summary visit information (e.g. lab)	
 • The last assessment within the window will be used. • Cases where the same parameter is recorded more than once on the same date will be handled as follows: 
 ○ If time of completion exists the earliest measurement will be used; ○ If time does not exist the measurement from the lowest CRF visit number will be used.
Post-baseline safety	Notable abnormalities (e.g. lab)	The most extreme measurement in the window will be used. Note this means a patient can have a notably high and notably low measurement within a window.

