3.1 Study design

This is a randomized, double-blind, active control, multicenter, parallel-group trial evaluating secukinumab monotherapy and adalimumab monotherapy in approximately 850 subjects with active PsA. A screening period of up to 8 weeks before randomization will assess subject eligibility (see Figure 3-1). Efficacy assessments will occur through Study Week 52. Two follow-up visits at Week 60 and 68 will occur thereafter. Total maximum study duration, including screening period, is up to 76 weeks.

At Baseline (BSL), subjects whose eligibility is confirmed will be randomized to one of two groups (1:1): Group 1 (secukinumab 300 mg) with approximately 425 subjects or Group 2 (adalimumab 40 mg) with approximately 425 subjects. In order to maintain the blind, both groups will receive 1 or 2 placebo s.c. injections to keep consistency in the number of injections at each dosing visit. Secukinumab (300 mg) is available in 2 x 1.0 mL pre-filled syringes (PFS) and adalimumab is available in 1 x 0.4 mL PFS. Placebo (1.0 and 0.5 mL PFS) is also available.

Group 1 - Secukinumab 300 mg s.c.

Secukinumab 300 mg (2 x 1 mL PFS) will be administered at Baseline, Weeks 1, 2, 3 and 4, followed by dosing every 4 weeks until Week 48.

In addition, all Group 1 subjects will receive placebo (1 x 1mL PFS) at given visits in order to maintain the blind (see Figure 3-1; Table 5-1).

Group 2 - Adalimumab 40 mg s.c.

Adalimumab 40 mg (1 x 0.4mL PFS) will be administered at Baseline followed by dosing every 2 weeks until Week 50.

[figure not shown]
In addition, all Group 2 subjects will receive placebo (1 x 0.5mL or 2 x 0.5mL PFS) at given visits in order to maintain the blind (see Figure 3-1; Table 5-1).

Study staff involved in drug handling and administration (e.g., investigational treatment receipt, inventory, storage, administration, and accountability) and IRT processes, will be unblinded and must not be the investigator or study staff involved in safety and efficacy assessments or eCRF completion. In addition, investigational treatment administered by the designated study staff member who is unblinded to treatment assignment must be done in a manner that maintains subject blinding as described in the Study Reference Manual. All other subject-related activities will be managed by blinded site personnel throughout the study.

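### The Week 52 efficacy window runs to Day 498 with a last-value rule, so an unscheduled efficacy measurement made during follow-up in a patient who completed dosing would override the true Week 52 result

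*SAP*

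**What the plan says.** **Window.** SAP 6.1, Table 6-1, gives Week 52 as Days 359–498 for Group 1 (ACR components, ESR, hsCRP) and Days 345–498 for Group 5 (LEI, PASI among others). Neither group has a later analysis visit.

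**What is mapped.** SAP 6.1: "The mapping described above applies to all visits (not just scheduled visits"). Repeat and unscheduled visits are treated like scheduled ones.

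**Which value is used.** SAP Table 6-2, post-baseline efficacy: "The last assessment within the window will be used". The reason given is the minimum dosing interval combined with two-weekly adalimumab dosing, "which leads to all visit delays accumulative".

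**Follow-up exclusion.** SAP 6.1: "For lab/ECG/vital signs, follow-up (F/U) visit is excluded from analysis visit mapping window". Efficacy data are not mentioned.

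**Schedule.** Protocol 3.1: "Efficacy assessments will occur through Study Week 52. Two follow-up visits at Week 60 and 68 will occur thereafter". Secukinumab is last scheduled at Week 48. Adalimumab is given at baseline, "followed by dosing every 2 weeks until Week 50".

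**Data after stopping treatment.** SAP 2.7, 6.2.1.2 and 6.2.2.4 set efficacy data to missing after treatment discontinuation, or after cDMARD use past Week 36. Binary endpoints then count as non-response. The protocol glossary defines treatment discontinuation as stopping before the planned completion date.

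**The concern.** The endpoint is response at Week 52, two to four weeks after the last scheduled dose. The window attached to it also covers the whole post-treatment follow-up. If a joint count, PASI, LEI or HAQ-DI is recorded at an unscheduled visit in that period, the last-value rule prefers it to a valid assessment at about Day 365.

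Selection works by parameter, so a late value of one ACR component could be combined with other components from the real Week 52 visit. Background treatment also differs by then, because protocol 5.5.7 allows NSAID, low-strength opioid and paracetamol regimens to change after Week 52.

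No other rule protects a patient who completes dosing. The set-to-missing steps concern premature discontinuation and cDMARD use. They cannot be read as applying after any end of dosing, since the Week 52 visit itself follows the last dose and would be erased.

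Group 1 feeds H1, H3 and H4, and Group 5 feeds H2 and H5, so any hypothesis in the hierarchy could be touched.

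**Working it through.** **1. The SAP's window formula.** "Upper Limit = 0.25*(Week number of current visit)* 7 + 0.75 * (Week number of next applicable visit)*7 + 1".

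- Group 1, Week 48 with next visit Week 52: 0.25×48×7 + 0.75×52×7 + 1 = 84 + 273 + 1 = 358, as tabulated. Week 52 therefore starts on Day 359.
- Group 5, Week 40 with next visit Week 52: 70 + 273 + 1 = 344, as tabulated. Week 52 therefore starts on Day 345.

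The formula reproduces every earlier limit in both groups (Week 2 gives 25.5, shown as 26). It cannot produce the Week 52 upper limit, because these groups have no next visit. Day 498 is what it gives for Week 68 with a notional Week 72: 119 + 378 + 1 = 498. So Day 498 is read from the table and is not shown to be a miscalculation.

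For comparison, Week 52 with Week 60 as next visit gives 91 + 315 + 1 = 407. With Week 68 as next visit it gives 91 + 357 + 1 = 449, the limit tabulated for Groups 2 and 7.

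**2. Days** (study day = 7 × week + 1).

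| Event | Day | Days before Day 498 |
|---|---|---|
| Last scheduled secukinumab dose, Week 48 | 337 | 161 |
| Last scheduled adalimumab dose, Week 50 | 351 | 147 |
| Week 52 | 365 | 133 |
| Week 60 | 421 | 77 |
| Week 68 | 477 | 21 |

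The Week 52 window is 498 − 359 + 1 = 140 days wide for Group 1 and 498 − 345 + 1 = 154 for Group 5. Group 1 windows for Weeks 8 to 48 are 28 days wide.

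**3. The plan's power.** Inputs from protocol 9.7: 425 per arm, 62% against 50%, two-sided 0.05. Power = Φ[(d − 1.96·se₀)/se₁].

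- se₀ = √(0.56×0.44×2/425) = 0.0341
- se₁ = √((0.62×0.38 + 0.50×0.50)/425) = 0.0338
- (0.12 − 0.0667)/0.0338 = 1.58, so power is 94.2%. The stated 94% reproduces.

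**4. Size if overwriting occurs.** The documents give no frequency. Assume that a share f of true ACR20 responders is overwritten to non-response, so an affected arm's rate becomes p(1 − f). Each cell shows the difference in percentage points, then the power.

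| f | Both arms | Secukinumab only | Adalimumab only |
|---|---|---|---|
| 0 | 12.0; 94.2% | 12.0; 94.2% | 12.0; 94.2% |
| 1% | 11.9; 93.8% | 11.4; 91.8% | 12.5; 95.8% |
| 2% | 11.8; 93.3% | 10.8; 88.5% | 13.0; 96.9% |
| 5% | 11.4; 91.6% | 8.9; 74.1% | 14.5; 99.0% |

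In the last column the rise reflects an inflated difference, not a real gain. At f = 5% the number overwritten would be 0.05×0.62×425 ≈ 13 secukinumab patients or 0.05×0.50×425 ≈ 11 adalimumab patients.

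**The case against.** **No efficacy assessment is planned after Week 52.** Protocol 3.1 says so. In protocol Table 6-1, as far as the broken columns can be read, the last follow-up columns carry only concomitant medication and adverse events. Protocol section 11 bars additional data collection for research. Day 498 can then be seen as an end-of-study cap. This stands, and it limits the point to unscheduled measurements. It does not remove the point, because SAP 6.1 expects unscheduled visits and maps them.

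**The last-value rule has a purpose.** If a Week 48 visit slips to Day 359 or later, taking the last value correctly prefers the true Week 52 visit. This stands, and any fix must preserve it.

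**Early discontinuers are unaffected.** Their binary results are non-response whatever is recorded later, and their later HAQ-DI data are set to missing. This also stands.

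**Stronger readings that the documents do not support.**

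- A reader might infer that follow-up values routinely replace Week 52. The schedule rules that out.
- A reader might infer that substitution runs from response to non-response because patients return when they flare. That is plausible, but the documents say nothing about it, and a late value may be better or worse.
- A reader might infer bias between arms from different speeds of offset. The documents compare no offset rates, and protocol 5.5.5 notes that adalimumab elimination may take up to four months.
- A reader might take a single repeat CRP as the typical case. hsCRP is a central-laboratory test whose treatment-period results are withheld until database lock. It may fall under the laboratory exclusion, and it is one of five measures of which three must improve.

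**Conclusion.** The gap is real but narrow. As written, the SAP would let an efficacy value recorded after the Week 52 visit, in a patient who completed dosing, replace the Week 52 value of that parameter. The value could date from up to 161 days (secukinumab) or 147 days (adalimumab) after the last scheduled dose. Nothing in the mapping, missing-data or discontinuation rules clearly prevents this, except arguably for hsCRP.

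The impact is probably small. With 1% to 5% of responders overwritten in both arms, power falls from 94.2% to between 93.8% and 91.6%. Overwriting confined to one arm would shrink or inflate the difference, depending on the arm. These figures rest on assumed shares and on the assumption that every overwritten responder becomes a non-responder. They illustrate sensitivity and do not forecast a bias. The case for a change is that the primary endpoint should not depend on whether unscheduled visits happen, and that the cost is minimal.

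**What to change.** In SAP 6.1 and Table 6-2, for efficacy parameters:

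1. For patients who did not discontinue early, use the scheduled Week 52 visit assessment whenever it exists, even if late. Do not map efficacy assessments made after it.
2. If there is no Week 52 visit, keep the last-assessment rule but close the window before Week 60, at Day 407 by the SAP's own formula. A closest-to-Day-365 rule is not advised here, because it could select a delayed Week 48 visit over a later one.
3. State that an early End-of-Study visit is not labelled Week 52 for analysis. Protocol section 6 makes it correspond to the Week 52 visit, so this needs saying. It keeps the window of its actual day and the existing discontinuation rules.
4. Keep later values in listings.

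The cost is one derivation rule, settled before unblinding. It needs no new data, loses no scheduled assessment, and keeps the protection against accumulated visit delays.
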